15.1 Definition of Adverse events (AE)

Adverse Events are defined as any untoward medical occurrence, unintended disease or injury or any untoward clinical signs (including abnormal laboratory finding), in subjects, users or other persons whether or not considered related to the investigational medical device.

NOTE 1: This definition includes events related to the investigational device or the comparator.

NOTE 2: This definition includes related to the procedure involved.

NOTE 3: For users or other persons, this definition is restricted to events related to Investigational medical device

15.1.1 Adverse device effects (ADE)

Adverse event related to the use of an investigational medical device.

Note 1 This includes any adverse event resulting from insufficiencies or inadequacies in the instruction for use, the deployment, the implantation, the installation, the operation, or any malfunction of the investigational medical device.

Note 2 This includes any event that is a result of a use error or intentional abnormal use of the investigational medical device.

15.1.2 Serious adverse events (SAE)

Adverse Event that:

- a. Leads to a death, injury or permanent impairment to a body structure or body function
- b. Leads to a serious deterioration in the health of the subject, that either resulted in:
 1. a life-threatening illness or injury or
 2. a permanent impairment of a body structure or a body function, or
 3. in-patient hospitalisation or prolonged hospitalisation,
 4. in medical or surgical intervention to prevent life-threatening illness
- c. Leads to foetal distress, foetal death or a congenital abnormality or birth defect

15.1.3 Pregnancy

If women become pregnant during the study she must be excluded from further study related examinations and follow-up visits.

The investigator should report all pregnancies within 24 hours of awareness to the sponsor.

The pregnant subject will be followed until the end of the pregnancy. The outcome of the pregnancy must be reported on the pregnancy report form. Any spontaneous abortion, stillbirth, birth defect/congenital anomaly, death or other serious infant condition must be reported and followed up as an SAE.

15.1.4 Serious adverse device effects (SADE)

Adverse device effect that has resulted in any of the consequences characteristic of a serious adverse event.

15.1.5 Unanticipated Serious adverse device effects (USADE)

Serious adverse device effect which by its nature, incidence, severity or outcome has not been identified in the current version of the risk analysis report.

Note: Anticipated serious adverse device effect (ASADE) is an effect which by nature, incidence, severity or outcome has been identified in the risk analysis report.

15.1.6 Device deficiencies (DD)

Inadequacy of an investigational medical device related to its identity, quality, quality, reliability, safety or performance. This may include malfunctions, use error, or inadequacy in the information supplied by the manufacturer.

15.1.7 Reporting of Adverse Events/Adverse Device Effects

All subjects will be carefully monitored for the occurrence of AEs during the investigation period from the run-in to the completion of follow up. The Clinical Investigator will collect AE information using non-leading questions such as "have you experienced any new health problems or worsening of existing conditions". Events directly observed or spontaneously volunteered by subjects will also be recorded.

Clearly related signs, symptoms and abnormal diagnostic procedure results should be grouped together and reported as a single diagnosis or syndrome whenever possible.

All AEs including but not limited to events reported by the subject or reported in response to an open question by the Clinical Investigator or member of this team, which fall into any of the above definitions must be recorded as an AE in the eCRF and should include the following information.

- Brief description of the event (diagnosis)
- Start date (and time, if relevant)
- Stop date (and time, if relevant) (or resolution)
- Severity
- Action taken regarding the medical device
- Opinion on causality
- Seriousness
- Outcome

Severity will be assessed using the following definitions:

Mild	Aware of sign or symptom, but easily tolerated.
Moderate	Discomfort enough to cause interference with usual activity.
Severe	Incapacitating with inability to work or do usual activity.

The relationship to investigational device will be assessed by the Investigator using the following definitions:

Not related	Evidence exists that the adverse event definitely has a cause other than the investigational device (e.g. pre-existing condition or underlying disease, intercurrent illness, or concomitant medication) and does not meet any other criteria listed.
Unlikely	The relationship with use of the device seems not relevant and/or the event can be reasonably explained by another cause, but additional information may be obtained.
Possibly related	A temporal relationship exists between the event onset and use of investigational device. Although the adverse event may appear unlikely to be related to the investigational device, it cannot be ruled out with certainty; and/or the event cannot be readily explained by the subjects' clinical state or concomitant therapies.
Probably related	A temporal relationship exists between the event onset and administration of investigational device, and appears with some degree of certainty to be related based on known mechanism of action of the device. It cannot be readily explained by the subjects' clinical state or concomitant therapies.

Causal relationship (Definitely related)	Strong evidence exists that the investigational device caused the adverse event. There is a temporal relationship between the event onset and administration of the investigational device including user error. There is strong mechanistic evidence that the event was caused by the investigational device. The subject's clinical state and concomitant therapies have been ruled out as a cause.
---	---

Any AE's that are possibly, probably or definitely related will be classified as ADE.

15.2 Reportable events and Emergency contact details

All serious events:

- Any SAE
-
- Any Device Deficiency(DD) that might have led to a SAE if (a) suitable action had not been taken or b) intervention had not been made or c) if circumstances had been less fortunate
- New finding/updates in relation to already reported events

that occur during the investigation, including death, ***must be reported to the sponsor or its representative immediately (within one working day) but no later than 3 calendar days*** after investigators awareness of the event

The reporting will be performed electronically via the eCRF (Viedoc™). The site staff will log into Viedoc™ and enter all available information regarding the reportable even in the AE Log for the specific subject. As soon as the event is saved as "serious" in Viedoc™, an email alert will immediately be sent to the medical Monitor and AddBIO.

In case any additional documentation should be required, PCG will request this information from the study site. All reportable events must be followed until resolution or until the investigator assesses them as being under full control. .

In case the eCRF is out of order, or no internet access is available at the study site, the reportable event should be reported using a paper copy form, which will be available at the site and should be completed manually. The completed, signed and dated report should, within 24 hours, be faxed to:

PCG Clinical Services AB
Att: PCG Pharmacovigilance
[contact]

The study site should notify the local CRA via phone or email about the submission of the SAE report. As soon as the personnel have access to Viedoc™, the SAE should be reported electronically as well

Sponsor will follow the procedures for reportable events to the Competent Authority as outlined in MEDDEV 2.7/3 revision 3 May 2015 and must report to Competent Authority immediately, but no later than 2 calendar days after awareness for any event that is death, serious injury, or serious illness and that requires remedial action for subject, users or other person.

Any other new finding/update, immediately, but no later than 7 calendar days following the date of awareness of the sponsor.

The investigator agrees to cooperate with the monitor to ensure that any problems detected in the course of these monitoring visits, including delays in completing the eCRFs are resolved.

All formal monitoring visits and/or other communication between Sponsor, Monitor, Investigator, or any other regulatory body (Ethics, CA) will be documented in specified format as per sponsor procedures and kept in accordance with ISO 14155 GCP Standard.

Full details regarding site monitoring will be covered in a separate Site Monitoring Plan (SMP) document.

16.1 Subject Records and Source Data

Data may be recorded directly in the eCRF, which will then be considered as source data. This must be documented in the SMP before the study starts.

The origin of source data in the investigation will be further specified in SMP ("Origin of Source Data").

It is the responsibility of the Clinical Investigator to record essential information in the medical records in accordance with national regulations and requirements, including:

- Investigation code
- Subject screening number and/or subject number
- That informed consent for participating in the study was obtained
- Diagnosis
- All visits during the investigation period
- All AEs/ADEs
- All SAE/SADES
- All DD
- Treatments and medications
- The identification of the device
- Location of Code envelopes

The Clinical Investigator is responsible for ensuring the accuracy, completeness, legibility and timeliness of the data recorded in the eCRFs. Signed sections of eCRFs will be monitored and collected on a regular basis.

16.2 Access to Source Data and Documentation

The Clinical Investigator should guarantee access to source documents for the monitor and auditors as well as for inspection by appropriate regulatory agencies, and the EC, if required.

17 Quality assurance

AddBIO is responsible for independent quality assurance (QA) audits of the clinical investigation processes, if deemed needed. Audit of the investigation sites may be conducted to assess and help assure the compliance with ISO 14155 GCP Standard and applicable regulatory requirements. The sites may be subject to a QA audit by the Sponsor or its representatives, as well as inspected by Competent Authorities (CA) and Ethical Committees (EC). This implies that auditors/inspectors will have the right to inspect the study sites at any time during and/or after completion of the investigation and must have access to source documents, including subjects' medical records. By participating and signing this CIP this the Investigator agrees to this requirement.

18 Statistical considerations

18.1 Statistical and analytical plans

The principal features of the statistical analysis of the data are described in this section. A more technical and detailed elaboration of the principal features will be written in a separate statistical analysis plan (SAP) and is to be finalised prior to database lock Part I. When the investigation up to week 12 is completed and the data are assembled, a blinded review of the planned analysis in Part I at the clean file meeting will be carried out. The review will concern the definition of outliers, violators, and exclusion of subjects or data from the analysis sets. Decisions made in connection with

the review will be documented. The SAP will be reviewed and could be updated as a result of the review of the data. The database lock to Part I will contain only study variables measured up to and include visit week12. Tables, figures and CSR to Part I will be based on this first database lock.

When study Part II is completed and the data are assembled, a new blinded review for Part II will be carried out at this second clean file meeting. The second database lock will be performed for Part II based on data after 12 weeks visit. The final CSR will be based on all locked data.

18.2 General methodology

The design of the study is a two parallel group design. The main efficacy analyses will be performed on the Intention-to-Treat (ITT) populations between the two groups. Complementary performance analyses will be performed on the Per Protocol (PP) population. See section 18.4 below.

For comparison between the two randomized groups regarding “index implant”, Fisher’s non-parametric permutation test will be used for continuous variables, Mantel-Haenszel chi-square test for ordered categorical variables, and Chi-square test for non-ordered categorical variables and Fisher’s exact test for dichotomous variables.

For primary efficacy variables and for other important continuous efficacy variables the 95% confidence interval for the mean difference between the two groups will be obtained by inversion of Fisher’s non-parametric permutation test by means of simulation.

For comparison between the two randomized groups regarding analysis of all teeth within subjects a mixed model with random effects analysis adjusting for within subject correlation will be used.

If significant clinical relevant differences are found between the two randomised groups in important baseline variables, then complementary efficacy analyses will be performed adjusted for these variables.

For comparison over time within randomized groups Fisher’s non-parametric permutation test for paired observations will be used for change in continuous and Sign test for change in ordered categorical variables or change in dichotomous variables.

The distribution of the variables will be given as mean, SD, median, minimum and maximum for continuous variables and as number and percentages for categorical variables.

Time to loss of implant will be described with Kaplan-Meier curves and analysed with Log-rank test between the two randomised groups.

All significance tests will be two-sided and conducted at the 5% significance level.

18.3 Statistical hypothesis

Primary Objective – the hypothesis is that there will be improved early stability of the “index implant” observed with the coated than with the uncoated implants, determined with change in ISQ values from day 1 to 12 weeks after insertion.

Secondary Objectives – the hypothesis is that there will be improved early stability of the “index implant” observed with the coated than with the uncoated implants, determined with change in ISQ values from day 1 to 8 weeks after insertion.

Furthermore— the hypothesis is that there will be improved early stability of all implants observed with the coated than with the uncoated implants, determined with change in ISQ values from day 1 to week 8 and 12 after insertion and determined with ISQ values at week 8 and week 12.

The hypothesis is also that there will be less marginal bone loss for coated compared to uncoated implants from implantation to week 8 and 12.

At the post follow-up visits at month 12 and 24 it is anticipated that this difference will be greater in the maxillary teeth as mandibular bone is usually of better quality. At month 12 and 24 post follow-up compare safety, survival rate and change in marginal bone height from implantation between coated and uncoated implants.

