9.7 Risk-Benefit conclusion
The major benefit of the Zolidd One ExHex implant is expected to be a shortening of the time for healing while giving a stable implant in areas where the bone quality is not optimal. Risks have been mitigated as far as possible and the risk-benefit ratio of using Zolidd One ExHex for partial edentulous subjects participating in this investigation is judged to be favourable (benefit is higher than risk).

10 Objectives and hypotheses for the clinical investigation

The objective of this investigation is to evaluate the efficacy and safety of Zolidd One ExHex implants when used for the intended purpose. Primary evaluation will be week 12 after implantation at end of Study Part I. Data will continue to be collected at month 12 and 24 for a second analysis at 24 months after implantation as part of the Post Follow-up of the device Part II.

Where a subject receives more than one implant, the most posterior maxillary implant will be considered to be the “index implant”, which will be assessed for performance as primary objective. In a case where the subject also has mandibular implants more posterior than the most posterior maxillary implant the maxillary implant will still be considered to be the “index implant”.

In a case where subject have bilateral teeth in same location the investigator will be free to select one of these teeth to be the “index implant”, but will document his reasoning for selection before implantation and shall be recorded in eCRF.

All implants will be followed regardin safety and performance (efficacy) however the “index implant” will as primary be comparing coated and uncoated devices

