##### The secondary objectives Part II:

- To compare safety as assessed by complications post-surgery and other adverse events up to month 24 post-implantation visit between all coated and all uncoated implants
- To compare survival rate of implants up to 24 months between all coated and all uncoated implants
- To compare change in marginal bone height from day 1 to month 12 and 24 between all coated and all uncoated implants
- To compare signs of peri-implantitis frequency at 12 and 24 months between all coated and all uncoated implants.

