## 4 STATISTICAL METHODOLOGY

### 4.1 General Methodology

The design of the study is a two parallel group design. All main efficacy analyses will be performed on the ITT population. Complementary efficacy analyses will be performed on the PP population.

For comparison between the two groups (coated vs uncoated), when we have only one observation per subject, Fisher's non-parametric permutation test will be used for continuous variables, Fisher's exact test for dichotomous variables, Mantel-Haenszel chi-square test for ordered categorical variables and Chi-square test for unordered categorical variables.

For primary efficacy variables and for other important continuous efficacy variables the mean difference between the two groups with 95% confidence interval (CI) will be given. For dichotomous variables the percentage in each group together with the difference in percentage between the two groups with 95% confidence interval will be calculated with Miettinen and Nurminen's method.

If clinically relevant significant differences are found between the two randomised groups in important baseline predictors a complementary primary efficacy analyses will be performed

STATISTISKA KONSULTGRUPPEN		Statistical Analysis Plan	
Protocol: A randomized, double blind, parallel study to evaluate the performance and safety of the Zolidd One ExHex dental implant in subjects with partial edentulism		Protocol No: ADD-001	Version: 1.0 Page 11 of 18

adjusted for these variables using analysis of covariance (ANCOVA) for continuous outcome variables and with multivariable logistic regression for dichotomous outcome variables.

For comparison between the two groups (coated vs uncoated), when we have more than one observation for all or for some subjects, a mixed model with random effects will be used for continuous outcome variables and a General Estimating Equation (GEE) model is used for dichotomous outcome variables. In both these models the dependence within observation are taken into account correctly. For non-normal continuous variables the mixed model will include an empirical bias correction with robust standard errors.

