For comparison over time of index implants within randomized groups Fisher's non-parametric permutation test for paired observations will be used for change in continuous and Sign test for change in ordered categorical variables or change in dichotomous variables. When all implants are analyzed the same methods as specified above, i.e. mixed and GEE models will be applied.

The distribution of the variables will be given as mean, SD, median, minimum and maximum for continuous variables and as number and percentages for categorical variables.

The survival rate of implant (implant loss) will be described with Kaplan-Meier curves with 95% CIs adjusted for within-subject correlation and analyzed with suitable Log-rank test, also adjusted for within-subject correlation, between the two randomised groups.

All tests will be two-tailed and conducted at 0.05 significance level. All analyses will be performed by using SAS® v9.2 (Cary, NC).

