#### 4.8.3 Secondary Efficacy Analyses Part II

Secondary efficacy analyses for Part II will be the comparison between the two randomized groups regarding all the secondary efficacy variables given in section 3.2.3 using the statistical methodology given in sections 4.1 above on the ITT-population.

Complementary analyses between the two randomized groups of secondary efficacy variables will be done on the PP-population.

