#### 4.8.5 Subgroup Analyses

Interaction analyses will be performed between baseline variables and group effect, coated vs uncoated, regarding primary efficacy variable on the ITT population.

Interactions effect with ( $p < 0.10$ ) will be followed by suitable subgroups analyses for that baseline variable.

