## 7.2 Listing of Figures

Figure Number	Table Title
14.2.1	Box-Plots of max ISQ values for day 1, week 8 and week 12 by treatment group (ITT Population)
14.2.2	Box-Plots of max ISQ values for day 1, week 8 and week 12 by treatment group (PP Population)
14.2.3	Box-Plots of change in max ISQ values from day 1 to week 8 and week 12 group (ITT Population)
14.2.4	Box-Plots of change in max ISQ values from day 1 to week 8 and week 12 group (PP Population)
14.2.5	Box-Plots of marginal bone height for day 1, week 12, month 12 and month 24 by treatment group (ITT Population)
14.2.6	Box-Plots of marginal bone height for day 1, week 12, month 12 and month 24 by treatment group (PP Population)
14.2.7	Box-Plots of change in marginal bone height from day 1 to month 12 and month24 by treatment group (ITT Population)
14.2.8	Box-Plots of change in marginal bone height from day 1 to month 12 and month 24 by treatment group (PP Population)

Protocol:

**A randomized, double blind, parallel study to evaluate  
the performance and safety of the Zolidd One ExHex  
dental implant in subjects with partial edentulism**

Protocol No:

ADD-001

Version:

1.0

Page 17 of 18

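### The protocol expects a larger coating effect in the upper jaw at months 12 and 24, but no planned Part II output gives the coated-uncoated difference by jaw (minor)

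*Protocol*

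**What the plan says.** Protocol 18.3 first sets out hypotheses on stability to weeks 8 and 12, then one on marginal bone loss to weeks 8 and 12. It continues: "At the post follow-up visits at month 12 and 24 it is anticipated that this difference will be greater in the maxillary teeth", and gives better mandibular bone quality as the reason. Its next sentence names the month 12 and 24 comparisons (safety, survival and bone-height change, coated against uncoated) without mentioning jaw.

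The SAP states the Part II bone-height objective as "To compare change in marginal bone height from day 1 to month 12 and 24 between all coated and all uncoated implants". SAP 4.8.3 adds: "Secondary efficacy analyses for Part II will be the comparison between the two randomized groups regarding all the secondary efficacy variables". Under SAP 4.1, where subjects contribute several implants, "a mixed model with random effects will be used for continuous outcome variables" and GEE is used for dichotomous outcomes. For implant loss, "The survival rate of implant (implant loss) will be described with Kaplan-Meier curves with 95% CIs adjusted for within-subject correlation", with a correspondingly adjusted log-rank test. The listed bone-height figures are of the type "Box-Plots of change in marginal bone height from day 1 to month 12 and month24 by treatment group".

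On effect modification, SAP 4.8.5 says: "Interaction analyses will be performed between baseline variables and group effect, coated vs uncoated, regarding primary efficacy variable on the ITT population". Protocol 18.13 has the same scope. Protocol section 10 fixes the index implant: "the most posterior maxillary implant will be considered to be the" index implant, even when a mandibular implant lies further back.

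**The concern.** The sentence in 18.3 is about how the treatment effect varies between jaws. A comparison that pools the jaws cannot speak to it, and neither can a model that only relates implant position to outcome. As planned, the Part II report could neither support nor contradict an expectation written under the heading of statistical hypotheses, although implant position and bone height are both collected. If someone wanted the answer later, the by-jaw analysis would be post hoc.

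There is also a point of interpretation. If the effect does differ by jaw, the pooled bone-height difference remains a valid average, but its size depends on the mix of jaws among the implants placed.

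**Working it through.** **Each planned output checked for a by-jaw treatment effect**

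- *Part II comparisons* (protocol 18.5.3; SAP 1.1, 3.2.3, 4.8.3): all coated against all uncoated implants. No jaw stratum or treatment-by-jaw term in the mixed model, GEE or log-rank test (SAP 4.1).
- *Interaction and subgroup analyses* (protocol 18.13; SAP 4.8.5): primary variable only, that is, ISQ change to week 12 on an always-maxillary implant. Even if read as covering all implants, they stop at week 12.
- *Predictor analyses* (protocol 18.5.4; SAP 4.8.4; table 14.2.2.2): implant position is a candidate and the table reaches 24-month bone height. This gives the association of position with outcome. No interaction with treatment is described.
- *Figures* (SAP 7.2): bone height by treatment group only.
- *Position summary* (SAP 4.6): implant position per arm, so the jaw mix is shown, but not the effect by jaw.
- *Changes from protocol* (SAP 6): the jaw expectation is not mentioned.

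**The plan's own sample size**

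Inputs: difference 5 ISQ, SD 5.6, two-sided 0.05, power 90% (protocol 18.8; SAP 1.4). The normal formula gives n = 2 × (1.960 + 1.282)² × 5.6² / 5² = 26.4, so 27 per group. With the noncentral t, power is 0.896 at 27 and 0.907 at 28. The stated 28 is reproduced.

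**Precision of a by-jaw estimate**

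The documents give neither the mandibular share nor an SD for bone height, so results are in SD units of bone-height change. Assumptions:

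- 28 evaluable subjects per arm. This is the week-12 ISQ figure carried over to months 12 and 24.
- a = 1 to 3 maxillary implants per subject (the protocol allows 1 to 6 implants in total).
- k = 6, 11 or 17 subjects per arm (about 20%, 40% and 60% of 28) who also have b = 1 to 3 mandibular implants.
- Exchangeable within-subject correlation ρ = 0.2 or 0.5.

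Generalised least squares information per arm for (maxilla, mandible):

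- A subject with maxillary implants only adds a / (1 + (a−1)ρ) to the maxillary entry.
- A subject with both adds [diag(a, b) − ρ/(1 + (a+b−1)ρ) × vvᵀ] / (1−ρ), with v = (a, b).
- The variance of the two treatment effects is 2 × the inverse of the summed matrix.

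Worked case, a = b = 1, k = 6, ρ = 0.2:

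- Each two-jaw subject adds 1.0417 on the diagonal and −0.2083 off it.
- The arm total is [[22 + 6.25, −1.25], [−1.25, 6.25]], with determinant 28.25 × 6.25 − 1.25² = 175.
- Mandibular weight in the pooled effect = (6.25 − 1.25) / (28.25 + 6.25 − 2 × 1.25) = 5/32 = 0.156.
- SE(treatment × jaw) = √(2 × (6.25 + 28.25 − 2 × 1.25)/175) = √0.366 = 0.605.
- Detectable with 80% power: (1.96 + 0.84) × 0.605 = 1.69 SD.
- SE(mandible) = √(2 × 28.25/175) = 0.568; half-width 1.96 × 0.568 = 1.11 SD.
- SE(maxilla) = √(2 × 6.25/175) = 0.267; half-width 0.52 SD.

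Over all combinations:

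| Mandibular implants in those subjects | Mandibular weight in pooled effect | SE (treatment × jaw) | Detectable at 80% power | Mandibular CI half-width |
|---|---|---|---|---|
| 1 | 6–36% | 0.28–0.61 | 0.8–1.7 SD | 0.6–1.1 SD |
| 2 | 9–51% | 0.22–0.48 | 0.6–1.4 SD | 0.5–0.9 SD |
| 3 | 12–60% | 0.19–0.43 | 0.5–1.2 SD | 0.4–0.8 SD |

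The maxillary half-width is about 0.4 to 0.5 SD throughout. For scale, the effect that the trial is sized for on its primary endpoint is 5/5.6 = 0.89 SD.

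**Day-1 adjustment (not a jaw matter)**

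With equal SD σ at both visits and correlation r, the change has variance 2σ²(1−r), and the day-1-adjusted residual variance is σ²(1−r²). The ratio is (1+r)/2, which is 0.75 to 0.90 for assumed r of 0.5 to 0.8.

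**The case against.** The strongest reply is that the sentence records an anticipation. The sentence after it states what will be compared at months 12 and 24, without jaw, and jaw appears in no objective or endpoint. That stands, and it limits the point to minor. A reader might infer that the trial leaves one of its objectives untested; the documents do not support that. What remains is that an expectation with a stated rationale, placed under statistical hypotheses, is neither assessed nor openly set aside.

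A reader might also infer that the mix of jaws behind the pooled difference will stay hidden. It will not, because SAP 4.6 summarises implant position for each treatment group.

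The endpoint is an inference. The preceding bone-loss sentence concerns weeks 8 and 12, not months 12 and 24. Bone loss is still the most natural reading, since ISQ is not measured after week 12, but implant loss or peri-implantitis cannot be excluded. No by-jaw output is planned for any of them.

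It is also fair that a by-jaw estimate would be weak and would seldom settle the question. That argues against a significance claim, not against an exploratory estimate with its interval. Finally, protocol 18.1 provides a further blinded review before the second lock, which offers an occasion to add the analysis but does not promise it.

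**Conclusion.** The point holds as a minor gap. No planned Part II analysis, table or figure estimates the coated-uncoated difference by jaw, although Protocol 18.3 expects it to be larger in the maxilla. That absence is certain from the text; that the expectation concerns marginal bone height is only the likeliest reading.

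The plan's sample size, primary test and pooled Part II comparisons are unaffected. It would be wrong to conclude that the pooled bone-height result is invalid: it is an average over the jaws, with the mandible carrying anywhere from 6% to 60% of the weight under the assumptions above. That range shows how little can be said before the jaw mix is known. With 28 evaluable subjects per arm, only treatment-by-jaw differences of about 0.5 to 1.7 SD would be detectable with 80% power, so any by-jaw result is exploratory. Fewer evaluable subjects at months 12 and 24 would widen the intervals.

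**What to change.** 1. State in Protocol 18.3 and in the SAP which endpoint the jaw expectation concerns.
2. If it is marginal bone height, add to SAP 4.8.3 and 4.8.5 one prespecified exploratory treatment-by-jaw term (jaw as a fixed effect, derived from implant position) in the all-implant mixed model for change to months 12 and 24. Report the coated-uncoated difference in each jaw with a 95% confidence interval, for example in table 14.2.3.2, and make no significance claim.
3. If implant loss or peri-implantitis is meant, tabulate it by jaw and arm descriptively.
4. If the sponsor wants neither, say in SAP section 6 that the jaw expectation will not be assessed.
5. As a separate improvement unrelated to jaw, adjust the bone-height model for the day-1 value.

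The cost is SAP wording, one exploratory term and one covariate, with no new data. SAP 1.2 analyses and locks bone height only once, at the end, so the term can be fixed before any bone-height comparison is seen. That safeguard does not extend to implant loss, because survival to week 12 is already analysed in Part I. The downside is imprecise per-jaw estimates, chiefly in the mandible. The primary analysis and the Part I models do not change.
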